5.2.2.4 Overall Survival

OS will be assessed using Kaplan-Meier methods from time of first treatment to death using the same methods described for PFS. Patients without documented death will be censored at last alive date. OS analysis will be repeated for the subset of enrolled Japanese patients.

5.2.2.5 Sum of Target Lesions

The best (minimum) percent change from baseline in sum of all target lesions will be summarized (mean, standard deviation, minimum, and maximum) for both IRC and investigator assessment of target lesions overall and by best overall response. A waterfall plot will be produced for each phase/treatment. Each subject's best percent change will be classified by best overall response (CR, PR, SD, PD).

5.2.3 Exploratory Efficacy Analyses

Logistic regression (ORR) and Cox regression models (time to event endpoints) may be used to explore the impact of prognostic factors and other important baseline characteristics on response. For each of these potential explanatory variables a simple model with each variable as the sole predictor will be run. In addition, models with multiple potential explanatory variables may be fit in the same model and model selection techniques used to examine which combination of variables best predict response (logistic regression models) or best describe the hazard function (Cox models). These exploratory analyses may or may not be presented formally. Further details on these analyses may be outlined in a separate analysis plan, and results may be summarized in a separate report.

5.3 Safety Analyses

5.3.1 Adverse Events

Adverse events will be coded using MedDRA Version 20.1 or higher. The severity grade of the TEAE will be assessed by the Investigator according to the NCI-CTCAE Version 5. If a TEAE is not included in the NCI-CTCAE definitions, the severity grade of the TEAE will be assessed by the Investigator according to the study protocols.

TEAEs will be summarized by phase and treatment by MedDRA system organ class (SOC) and preferred term (PT), or PT only. For summary tables by SOC and PT, SOC will be sorted alphabetically, and PT will be sorted by decreasing frequency within each SOC. For summary tables by PT only, PT will be sorted by decreasing frequency.

If multiple TEAEs of the same PT occur within a patient, only the maximum grade observed for this PT will be used in summary of TEAEs by grade; the patient will be counted only once per SOC and PT.

An overview TEAE summary table will be provided including the number of patients with AEs in selected categories. In addition, TEAEs will be summarized for the following categories, and will be tabulated by SOC and PT:

- TEAEs (All Grades, All Causalities)
- Treatment-related TEAEs (All Grades)
- TEAEs by maximum grade (All Causalities)
- Treatment-related TEAEs by maximum grade
- Grade 3 or higher TEAEs (All Causalities)
- Grade 3 or higher treatment-related TEAEs
- Treatment-emergent SAEs (All Causalities)
- Grade 3 or higher SAEs (All Causalities)
- Grade 3 SAEs (All Causalities)
- Grade 4 SAEs (All Causalities)
- Treatment-related treatment-emergent SAEs
- TEAEs resulting in discontinuation of study drug (All Causalities)
- TEAEs resulting in dose hold (All Causalities)
- TEAEs resulting in dose reduction for duvelisib (All Causalities)
- TEAEs resulting in any modification to study drug administration (All Causalities); defined as discontinuation, reduction, and/or dose hold
- TEAEs resulting in death (All Causalities)
- Treatment-related TEAEs resulting in death
- TEAEs by PT (All Grades, All Causalities)
- Treatment-related TEAEs by PT (All Grades)
- Grade 3 or higher TEAEs by PT (All Causalities)
- Treatment-emergent SAEs by PT (All Causalities)
- Treatment-related treatment-emergent SAEs by PT

Three tables summarized by SOC only will be provided, sorted by descending frequency:

- All TEAEs
- All SAEs
- All TEAEs leading to treatment discontinuation.

A by-patient listing of the following AE categories will be presented.

- All AEs (TEAEs will be flagged)
- All SAEs (TEAEs will be flagged)
- TEAEs resulting in dose hold
- TEAEs resulting in dose reduction
- TEAEs resulting in discontinuation of study drug
- TEAEs resulting in death

5.3.1.1 Other Adverse Events of Interest

Selected MedDRA PTs will be combined to create grouped PTs or categories to further characterize risks associated with duvelisib. The following risks will be summarized:

Grouped Term	Preferred Terms
Diarrhea	Diarrhoea, Diarrhoea hemorrhagic, Defecation urgency
Colitis	Colitis, Colitis erosive, Enterocolitis, Enterocolitis hemorrhagic, Colitis microscopic, Necrotising colitis, Colitis ulcerative
Pneumonia	Pneumonia, any PT containing the word/string "pneumonia" except for "Pneumonia aspiration", Atypical pneumonia, Atypical mycobacterial pneumonia, Bronchopneumonia, Bronchopulmonary aspergillosis
Pneumonitis	Pneumonitis, Interstitial lung disease, lung infiltration, acute interstitial pneumonitis
Transaminase elevation	Alanine aminotransferase increased, Aspartate aminotransferase increased, Transaminases increased, Hypertransaminasaemia, Hepatic enzyme increased, Acute hepatic failure, Drug-induced liver injury, Hepatic failure, Hepatocellular injury, Hepatotoxicity
Cutaneous reactions	Dermatitis, Dermatitis allergic, Dermatitis bullous, Dermatitis exfoliative, Dermatitis psoriasiform, Drug eruption, Drug reaction with eosinophilia and systemic symptoms, Erythema, Erythema multiforme, Generalised erythema, Exfoliative rash, Rash, Rash generalised, Rash erythematous, Rash follicular, Rash macular, Rash maculo-papular, Rash maculovesicular, Rash papular, Rash papulosquamous, Rash pruritic, Rash pustular, Rash vesicular, Toxic skin eruption, Palmar erythema, Palmoplantar keratoderma, Palmar-plantar erythrodysesthesia syndrome, Perivascular dermatitis, Skin reaction, skin toxicity, Stevens-Johnson syndrome, Toxic epidermal necrolysis
Neutropenia	Neutropenia, Neutrophil count decreased

The specific PTs that will be combined for each risk will be defined in the analysis dataset programming specifications.

For each risk, PTs will be summarized at the grouped PT and individual PT (and grouped SOC if applicable), at the patient level:

- TEAEs (All Grades, All Causalities)
- Treatment-related TEAEs (All Grades)
- Grade 1 or 2 only TEAEs (All Causalities)

- Grade 3 or higher TEAEs (All Causalities)
- Grade 4 TEAEs (All Causalities)
- TEAEs resulting in death (All Causalities)
- Treatment-emergent SAEs (All Causalities)
- Treatment-related treatment-emergent SAEs
- TEAEs resulting in dose hold (overall and by resolution)
- TEAEs resulting in dose reductions (overall and by resolution)
- TEAEs resulting in dose hold or reductions (overall and by resolution)
- TEAEs resulting in discontinuation of study drug (overall and by resolution)
- Time to initial onset (defined as AE start date first dose date +1)
- For all infections only a summary broken out by MedDRA High Level Terms (HLT) and High Level Group Terms (HLGT)
- TEAEs by time on treatment (up to 56 days, 57 through 112 days, > 112 days)

Only patients who entered the treatment period will be considered in summaries by treatment period (*i.e.*, if a patient withdrew from treatment between days 57 and 112 they would be included in the up to 56 days summary and in the 57 through 112 days summary, but not in the > 112 days summary).

In addition, the following summaries will be created for each grouped PT within each grouped SOC, at the event level:

- Duration of AE
- Time to Onset of AE

In addition, use of specific concomitant medications to treat each of the risks will be summarized. Concomitant medications can be associated with specific TEAEs in the clinical database, and for each adverse event of interest all medications associated with any preferred term in the group of terms will be summarized.

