# 1.4. Benefit/Risk Assessment

Clinical study results to date support a favorable benefit-risk of duvelisib for patients with hematologic malignancies. The risks are consistent with the AE profile for the PI3K inhibitor drug class and AEs experienced by patients undergoing treatment for advanced cancers. Important identified risks include infections, diarrhea/colitis, cutaneous reactions, pneumonitis, neutropenia, and ALT/AST elevation. Potential risks include hepatotoxicity, drug-drug interaction (DDI) and reproductive toxicity. These toxicities are managed using a combination of prophylaxis, supportive care and dose modifications. Duvelisib monotherapy has demonstrated encouraging activity in relapsed and refractory PTCL seen in this study and the Phase 1 study in hematologic malignancies. The starting dosage will be 75 mg BID until the first response assessment (2 cycles) in an attempt to debulk the tumor more efficiently. Subsequently, the dose will be reduced to 25 mg BID to anticipate and reduce toxicities of later times of onset. As both dose levels have demonstrated preliminary responses, this strategy is designed to reduce the risk of toxicity while maintaining clinical benefit. Overall, the potential benefit to a patient

with relapsed/refractory PTCL with few treatment options and historically a dismal prognosis, appears at this time, to outweigh any potential risks.

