#### 9.1.2. Expansion Phase

The duvelisib dose in the Expansion Phase will be:

Duvelisib PO at 75 mg BID for the first 2 cycles (cycle = 28 days) until the first response assessment (See Table 4). Then, dose will be reduced to 25 mg BID and administered in 28-day cycles.

If a subsequent assessment demonstrates progression and the patient did not require a dose modification due to toxicity, the dose can be re-escalated to 75 mg BID with a confirmatory scan after approximately 4 weeks of therapy. If the patient has progressive disease at the confirmatory scan, then the patient should be discontinued. Patients that re-escalate to 75 mg BID may remain at this dose level until the need for dose modification or the criteria for discontinuation is met.

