#### **11.4.** Populations for Analysis

The populations used for analysis will include the following:

- Dose Optimization Efficacy Population, consisting of all patients who 1) receive at least one dose of study drug and 2) complete at least one cycle of treatment and 3) have at least one scan to assess disease response after completion of one cycle of treatment
- The Safety Population, consisting of all patients receiving at least 1 dose of duvelisib

• The mITT Population, consisting of all patients who receive at least one dose of duvelisib which will be used for the Expansion Phase primary and secondary analyses as well as all safety analyses

All patients enrolled into the study will be included in data listings. All primary and secondary analyses will be performed separately for patients in the Dose Optimization and Expansion phases. Additional analyses combining patients from the Dose Optimization and Expansion phases may be performed as applicable. Further details will be provided in the SAP. Summary statistics will be produced by dose level, for patients with dose changes and for the overall study population for both safety and biological effect parameters.

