4.1 General Methods

Summary statistics will be presented by treatment group, unless stated otherwise.

Unless otherwise specified, descriptive statistics for continuous data will include the number of subjects with data to be summarized (n), mean, standard deviation, 25% quartile, median, 75% quartile, and minimum and maximum. The same number of decimal places as in the raw data will be presented when reporting the minimum and maximum, one more decimal place than the raw data will be presented when reporting mean and median, and 2 more decimal places than the raw data will be presented when reporting standard deviation.

Descriptive statistics for categorical/qualitative data will include frequency counts and percentages. The total number of subjects in the treatment group will be used as the denominator for percent calculations, unless stated otherwise. All percentages will be presented with one decimal, unless otherwise specified. Percentages equal to 100 will be presented as 100, and percentages will not be presented for zero frequencies.

Descriptive statistics associated with time-to-event analyses will include the number of events, the number of subjects censored, 25% quartile, median, 75% quartile, and 95% confidence interval for median. These statistics will be presented for all time-to-event analyses, unless stated otherwise.

Listings will be provided for selected endpoints.

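### In the adverse-event summary by time on treatment, the open-ended > 112-day percentage is not comparable with the two 56-day percentages and should be accompanied by exposure-adjusted rates

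*SAP*

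**What the plan says.** SAP 5.3.1.1 lists, for each grouped risk (diarrhea, colitis, pneumonitis and so on), a summary of "TEAEs by time on treatment (up to 56 days, 57 through 112 days, > 112 days". It fixes the denominator: "Only patients who entered the treatment period will be considered in summaries by treatment period". The summaries in that list are made for grouped and individual preferred terms "and grouped SOC if applicable), at the patient level". The bullet does not name the statistic, so the general rule in SAP 4.1 applies: "Descriptive statistics for categorical/qualitative data will include frequency counts and percentages".

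The first cut-point coincides with the planned dose change. Protocol 9.1.2 sets the Expansion Phase dose as "Duvelisib PO at 75 mg BID for the first 2 cycles (cycle = 28 days) until the first response assessment", then 25 mg BID, with re-escalation to 75 mg BID possible on later progression. Protocol 1.4 gives a safety reason for the change: "Subsequently, the dose will be reduced to 25 mg BID to anticipate and reduce toxicities of later times of onset". Protocol 4.3 sets no maximum duration of therapy, so the third period has no planned end.

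On dose, Protocol 11.4 states: "Summary statistics will be produced by dose level, for patients with dose changes and for the overall study population", for safety and biological effect parameters. SAP 5.3.1 states: "TEAEs will be summarized by phase and treatment by MedDRA system organ class" and preferred term.

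**The concern.** Restricting the denominator to entrants removes patients who had already left, but it does not adjust for how long each entrant is observed within the period. In the first two periods that time on treatment is capped at 56 days. In the third it is whatever the patient accrues. A patient-level percentage rises with time at risk even when the hazard is constant or falling, so the three figures are not on one scale.

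This matters more here than in a routine safety table. The regimen was chosen partly to limit later-onset toxicity, safety is a secondary objective, and the periods are cut at the dose change. A reader will naturally look along the row from the first period to the last to judge whether late toxicity fell, and the last column is the one that can mislead.

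**Working it through.** **No plan figure to reproduce.** The SAP gives no expected rate for this table. The cut-points do check: 2 × 28 = 56 days, and days 57 to 112 are another 56 days.

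**Assumptions (none is in the documents).** Time on drug is exponential with rate v = ln 2 / median. The event hazard is h per month up to Day 56 and h/2 afterwards. Medians run from 1.5 to 6 months and h from 0.03 to 0.12 per month. Onsets in the 30 days after last dose are ignored at first.

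**Formulas.** L = 56/30.44 = 1.840 months. Expected share of entrants with an event:
- closed 56-day period with hazard k: k/(k+v) × [1 − exp(−(k+v)L)]
- open period with hazard k: k/(k+v)

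**Worked case: median 3 months, h = 0.08.** v = 0.2310.
- Days 1–56: 0.08/0.3110 × (1 − 0.564) = 11.2%.
- No change in hazard: 11.2% in days 57–112, and 0.08/0.3110 = 25.7% after Day 112.
- Hazard halved after Day 56: 0.04/0.2710 × (1 − 0.607) = 5.8% in days 57–112, and 0.04/0.2710 = 14.8% after Day 112.

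So a halved hazard shows correctly in the second period (5.8% against 11.2%), yet the third period still exceeds the first (14.8% against 11.2%).

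**Hazard halved after Day 56, over the grid:**

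| Median on drug | Second ÷ first period | > 112 days ÷ first period |
|---|---|---|
| 1.5 months | 0.51–0.52 | 0.85–0.87 |
| 2 months | 0.51–0.53 | 1.00–1.04 |
| 3 months | 0.51–0.53 | 1.27–1.39 |
| 4 months | 0.51–0.53 | 1.51–1.73 |
| 6 months | 0.51–0.53 | 1.91–2.37 |

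With no change in hazard, the > 112-day to first-period ratio is 1.7 to 4.3 for medians of 2 to 6 months.

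**Break-even.** If every patient had the same fixed time at risk, the third percentage would overtake the first once time beyond Day 112 exceeds 112 days, because half the hazard needs twice 56 days. Under exponential discontinuation the break-even median is about 57 to 65 days, for first-period risks of 5% to 30% over a full 56 days.

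**Sensitivity to SAP conventions**, assuming a 20% risk over a full 56 days:
- Counting onsets up to 30 days after last dose (SAP 4.2), the first and > 112-day percentages are 18.8% and 19.7% at a 2-month median, and 19.6% and 38.2% at 6 months.
- The SAP does not say whether a patient with an earlier event counts again. If only first-ever onsets count while all entrants stay in the denominator, the fixed-time break-even rises from 112 to about 165 days.

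**What a rate would show.** In simulation under the same 20% risk, events per patient-year were about 1.46 in days 1–56, and 0.73 in days 57–112 and after Day 112. This held for medians of 2 to 12 months, with or without the 30-day tail. The halving is recovered in both later periods. In the worked case the corresponding rates are 8 and 4 per 100 patient-months.

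**The case against.** The strongest reply is that the table already answers the question where it can. The two 56-day periods straddle the step-down, and under the assumptions above that pair shows a halved hazard as a ratio of 0.51 to 0.53. This stands. A reader might infer that the whole table is uninterpretable or points the wrong way; the documents do not support that, and the problem is confined to the > 112-day column.

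It is also fair that reversal depends on treatment duration, on which the documents are silent. At a 2-month median there is no material reversal, and at 1.5 months the third column is lower than the first.

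A reader might infer that this is the only planned output bearing on late toxicity. It is not. SAP 5.3.1.1 also gives time to onset and duration of events, SAP 5.1.7 tabulates treatment duration in the same three categories, SAP 5.3.1.2 allows summaries by cumulative-dose quartile, and Protocol 11.10 leaves room for more safety analyses. None of these commits to a rate per time at risk, however. Time to onset describes only those with an event, exposure is tabulated apart from onset, and the other two are optional.

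Finally, a reader might infer that the SAP drops a promised analysis by dose at onset without declaring it. Protocol 11.4 asks for summaries by dose level but specifies neither dose at onset nor exposure adjustment. The synopsis places near-identical wording under the Dose Optimization Phase only, and reporting by phase and treatment is a plausible way to carry it out. That reading should not be pressed.

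The SAP plans no test between periods and the objective is to characterise safety, so this concerns how a descriptive table will be read.

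**Conclusion.** The point holds for the > 112-day column. Its percentage is not on the same footing as the two 56-day percentages, because the period is open-ended and the denominator is patients rather than time at risk. If the hazard is halved after Day 56, the > 112-day to first-period ratio is about 1.0 to 2.4 for assumed medians of 2 to 6 months and about 0.85 to 0.87 at 1.5 months. Late toxicity can therefore look higher when the risk has fallen; the documents do not show that it will. The figures rest on exponential time on drug, hazards of 0.03 to 0.12 per month and a single step in the hazard, all of which are assumptions. The primary endpoint is untouched. This is a worthwhile and cheap improvement to a table tied to the regimen's safety rationale.

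**What to change.** In SAP 5.3.1.1, keep the percentages and add for each period an exposure-adjusted rate: patients with a first event per 100 patient-months at risk in that period, with a 95% CI. State the counting rule: whether a patient with an event in an earlier period is at risk again, and how the 30 days after last dose enter the person-time.

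Optionally, give the same rates for the Expansion Phase by dose being taken at onset (75 mg, 25 mg, re-escalated 75 mg BID, held). This is one way to carry out the dose-level summaries in Protocol 11.4, which does not itself specify dose at onset.

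The cost is a few lines of SAP text and a few more tables, from adverse-event and dosing dates already collected. If the SAP is not reopened, Protocol 11.1 allows further modifications to be noted in the clinical study report. The rates stay descriptive: with no Expansion Phase group kept at 75 mg BID, they still mix dose with time on study and with selection of patients who stay on drug.

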5.3.1.2 Adverse Event Subgroup Analysis

Summaries of TEAEs and AESI by SOC and PT may be repeated for select subgroups including: sex, age group (<65 years, \geq 65 years), race, geographic region, cumulative dose quartiles, cumulative dose quartiles in cycles 1 and 2, and number of prior regimens (1,2, 3+). Cumulative dose quartiles will be based on doses for all patients in the safety analysis set with all treatment groups combined.

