5.1.7 Exposure to Study Drug

Extent of exposure will be summarized by phase and treatment based on the Safety Analysis Set.

Extent of exposure will be summarized for the following variables by cycle and overall:

- Duration (weeks): (date of last dose date of first dose + 1) divided by 7.
- Treatment duration categories (\leq 56 days, 57 112 days, > 112 days)
- Number of cycles started (continuous and categorical)
- Cumulative dose received (mg) (continuous and categorical by quartiles)
- Cumulative dose received (mg) during Cycles 1 and 2 (continuous and categorical by quartiles)
- Dose Intensity (mg/day) defined as total actual dose divided by duration in days
- Relative dose intensity, defined as 100% x (total dose received)/(planned cumulative dose for the duration of treatment)
- Average daily dose received (mg)
- Number and percentage of patients within Dose Optimization Cohort 1 with dose escalations to 50mg BID and 75mg BID
- Number and percentage of patients with a dose reduction
- Number and percentage of patients with a dose hold
- Number and percentage of patients for whom study drug was discontinued

Cumulative dose quartiles will be based on doses for all patients in the safety analysis set with all treatment groups combined.

For relative dose intensity, planned dose is defined as follows:

- Dose Optimization Cohort 1: 25 mg × 2 × total days treated at starting dose. For subjects whose assigned dose escalated due to SD at the end of Cycles 1 and 3 as described in the CSP, raise the planned dose accordingly.
- Dose Optimization Cohort 2: 75 mg \times 2 \times total days treated

Expansion Phase: 75 mg × 2 × (28 × 2) + 25 mg × 2 × (total days treated – (28×2)) if patient receives > 2 cycles of treatment *or* 75 mg × 2 × total days treated if patient received < 2 cycles of treatment.

Where total days treated = last dose date - first dose date + 1.

A by-patient listing will be presented for exposure to study drug. A separate listing of dose modifications will be provided for patients who received at least one dose modification.

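### AE percentages by cumulative-dose quartile mix dose with time on treatment and AE-driven dose changes, so with no dose effect they can rise, stay flat or fall

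*SAP*

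**What the plan says.** SAP 5.3.1.2 states that "Summaries of TEAEs and AESI by SOC and PT may be repeated for select subgroups including" two dose variables, "cumulative dose quartiles, cumulative dose quartiles in cycles 1 and 2". One set of cuts serves everyone: "Cumulative dose quartiles will be based on doses for all patients in the safety analysis set with all treatment groups combined".

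SAP 5.1.7 defines the grouping variable as total mg received, overall and during Cycles 1 and 2. The same section also has a per-day measure, "Dose Intensity (mg/day) defined as total actual dose divided by duration in days", but this is not an AE subgroup variable.

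In the Expansion Phase, total mg keeps rising after Cycle 2. Protocol 9.1.2 gives 75 mg BID for two cycles and continues: "Then, dose will be reduced to 25 mg BID and administered in 28-day cycles".

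The AE side works as follows. An event is treatment-emergent from first dose to last dose plus 30 days (SAP 4.2). Within a term, "the patient will be counted only once per SOC and PT" (SAP 5.3.1). Results are counts and percentages (SAP 4.1). No rate per unit of patient-time, landmark or time-varying dose analysis is specified.

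**The concern.** Time on treatment drives both the row and the column of this table. A patient who stays longer accumulates more mg and also has longer in which to be counted with an AE. There is a second path in the other direction: Protocol 8.1 and Table 8 let an AE stop, hold or reduce the drug, so the outcome helps decide the patient's quartile. The two paths pull in opposite directions, and their balance differs from one AE to the next.

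Protocol 1.3 and 1.4 justify the step-down to 25 mg BID partly by an expectation that later-onset toxicity can be reduced. A table of AEs by dose received is where a reader would look for evidence on that. This one cannot supply it, in either direction.

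**Working it through.** The plan gives no figure for these tables, so there is none to reproduce. The check asks what they would show if dose had no effect at all.

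**Inputs from the documents.** Expansion dosing is 150 mg/day to Day 56, then 50 mg/day. AEs count up to last dose + 30 days, once per patient. **Assumptions not in the documents:** constant AE hazard 0.08 per month; exponential time on treatment with median 3.5 months; no holds or reductions.

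1. *Dose quartile equals duration quartile.* For D days on drug, total dose is 150 × D up to Day 56 and 8,400 + 50 × (D − 56) after. This always increases with D, so without dose changes the dose quartiles are simply quartiles of time on treatment.

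2. *No AE stops the drug.* The median is 3.5 × 30.4 = 106.5 days, so the mean is 106.5 / ln 2 = 153.7 days. The mid-point durations of the four quartiles are −ln(1 − p) × 153.7 at p = 0.125, 0.375, 0.625, 0.875, which gives 21, 72, 151 and 320 days. The chance of being counted is 1 − exp(−0.08 × (D + 30) / 30.4), or about 13%, 24%, 38% and 60% at those points. Averaging over each whole quartile by simulation gives 13/24/38/62%. The rate per patient-month is 0.08 in every quartile. For median treatment of 2.5 to 5 months, the lowest quartile is 11 to 14% and the highest 52 to 74%.

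3. *Every on-treatment AE stops the drug.* The hazard of stopping for other reasons is ln 2 / 3.5 = 0.198 per month. The AE comes first with probability 0.08 / (0.08 + 0.198) = 0.288. A further 0.712 × (1 − exp(−0.08 × 30 / 30.4)) = 0.054 have it in the 30 days after stopping. The total is 0.34. With constant hazards this does not depend on when treatment ends, so every quartile shows 34%.

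4. *Half of on-treatment AEs stop the drug.* Simulation gives 25/28/34/50%.

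5. *AEs confined to early treatment.* This used a separate simulation of 130 Expansion, 16 Cohort 1 and 11 Cohort 2 patients with pooled quartiles, assuming a median of 90 days and a 20% AE risk by Day 56. If AEs occur only in days 1 to 56, the quartiles show 17/20/20/20% with no stopping and 30/24/11/11% if half stop the drug, which is an inverse gradient. With a constant hazard and no stopping, the same set-up gives 19/31/47/70%.

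6. *Cycle 1-2 quartiles.*
   - The planned maximum at 75 mg BID is 150 × 56 = 8,400 mg. If more than half of all pooled patients receive it, the median and the 75th percentile are both 8,400 mg and the upper two quartiles cannot be told apart.
   - A Cohort 1 patient who stays at 25 mg BID totals 50 × 56 = 2,800 mg. A 75 mg BID patient reaches that total at 2,800 / 150 = 18.7 days, so pooling puts two-cycle completers beside early stoppers.
   - In the simulation of step 5 (constant hazard, no stopping), the lowest quartile shows 26% against about 47% in the rest, because AEs are still counted over the whole treatment period.

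7. *Which remedies work.* With the inputs of step 4:
   - Person-time rates within whole-course dose quartiles run from 0.18 down to 0.06 per month, a false inverse trend.
   - Grouping by dose intensity up to first onset (150, 100 to 150, and under 100 mg/day) gives 0.34, 0.11 and 0.04 on treatment, or 0.23, 0.10 and 0.04 if the 30-day tail is included, against a true 0.08.
   - Assigning events and person-time to the dose being taken at the time gives 0.08 in both dose periods.

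**The case against.** The tables are optional (the SAP says they may be repeated), descriptive, and only two of seven listed subgroup variables. No decision rests on them, and the Expansion dose was already chosen from Dose Optimization data. For AEs of interest, SAP 5.3.1.1 already plans summaries by time on treatment (to 56 days, 57 to 112, over 112), limited to patients who entered each period, plus time to onset. The first cut falls on the planned dose reduction. All of this stands and keeps the point minor. It does not rescue the tables, because those summaries cover only AEs of interest and are not crossed with dose.

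A reader might infer that the tables would always show a strong rising dose-toxicity gradient. The documents do not support that. It needs AEs that do not change dosing, whereas Table 8 of the protocol withholds, reduces or stops drug for many of them. The gradient then weakens, and for early events it can reverse.

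A reader might also infer that the Cycle 1-2 version is equally affected, or that everyone who completes two cycles without a hold has received 8,400 mg. Neither follows. Its dose window is fixed, so time beyond Day 56 no longer raises the grouping variable. The 8,400 mg figure applies only to patients planned at 75 mg BID with no reduction or missed dose. The documents do not say how many patients that is, so the tie is conditional.

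**Conclusion.** The point holds as a minor one. AE percentages by quartile of total cumulative dose are confounded by time on treatment and by AE-driven dose changes. With no dose effect, the false pattern ranges from a steep rise (13% to 62%) through flat (34% throughout) to a fall (30% to 11%), depending on when the AE occurs and how often it stops the drug. The Cycle 1-2 version is less affected by duration but still carries whole-period AE counting, early stoppers in the low quartiles, mixing of cohorts, and a possible tie at the planned maximum.

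The direction follows from the SAP's own definitions. The sizes rest on the assumed hazards, treatment durations and stopping fractions, none of which the documents give. The rising pattern on its own is not established as what this trial would show.

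**What to change.** Replace the cumulative-dose quartile AE tables in SAP 5.3.1.2 with exposure-adjusted first-event rates:

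- Assign both events and person-time to the dose level being taken at the time (time-varying dose). State in advance how holds and the 30 days after last dose are handled.
- Present rates by phase or cohort starting dose and by period (to Day 56, after Day 56).
- If Cycle 1-2 dose is kept, use a landmark: AEs with onset after Day 56 among patients still on treatment, by Cycle 1-2 dose in categories that allow for a tie at the planned maximum.
- Do not group by dose intensity up to first onset, and do not compute person-time rates within whole-course cumulative-dose quartiles. Both depend on the outcome (step 7 of the working).
- State as a limitation that in the Expansion Phase dose level largely coincides with period, so dose and time cannot be fully separated.

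The cost is a change to the SAP text and modest extra programming on exposure and AE dates already collected. The descriptive exposure summaries in SAP 5.1.7 can stay as they are.
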